The primary efficacy endpoint of the study is the incidence of a composite of symptomatic ischemic stroke by Day 28 and unrecognized brain infarction at Day 28. Initially, randomization will be limited to the two lower doses of BMS-986141 (0.8 mg or 4.8 mg) or placebo in a 1:1:1 ratio until after DMC review of safety and laboratory data from the Day 28 study visit for at least 10% of planned total subjects (approximately 132 subjects). If the DMC recommends proceeding to inclusion of the highest dose (8 mg), subsequent randomization will be in a 1:1:1:1 ratio. Based on the staggered randomization and with a total of 1240 evaluable subjects, there is at least 80% power to demonstrate a dose-response relationship assessed by MCP-Mod method (see below), with Emax and logistic models included as candidate models, and using a 1-sided type I error of 15%. This assumes a true incidence for placebo of 14%, a maximum relative risk reduction of 30% for BMS 986141 8mg compared to placebo, and reductions of 75% and 90% of the maximum reduction for the 0.8 and 4.8 mg doses, respectively. To account for about 5% of subjects without post-randomization data, a total of 1312 subjects will be randomized.

Endpoints:

Primary efficacy endpoint

The primary efficacy endpoint of the study is the incidence of a composite of symptomatic ischemic stroke by Day 28 and unrecognized brain infarction assessed by MRI at Day 28.

Additional efficacy endpoints

Secondary endpoints:

- The incidence of major adverse cardiovascular events (MACE) by Day 90, defined as a composite of all adjudicated stroke, myocardial infarction, or CV death
- The incidence of the composite of adjudicated ischemic stroke, myocardial infarction, and CV death by Day 90
- The incidence of adjudicated symptomatic stroke (including fatal and non-fatal) by Day 28
- The incidence of the composite of unrecognized brain infarction assessed by MRI at Day 28 and MACE by Day 90

Primary safety endpoint

The primary safety endpoint will be incidence of a composite of adjudicated major bleeding and adjudicated CRNM bleeding during the treatment period.

Additional safety endpoints

- Additional safety endpoints include the incidence of adjudicated major bleeding events, all bleeding events, intracranial hemorrhage events, as well as the incidence of AEs and markedly abnormal standard clinical laboratory test results.

Analyses:

Adjudicated results will be the basis for the primary and secondary analyses.

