5 SAMPLE SIZE AND POWER

The primary efficacy endpoint of the study is the incidence of a composite of symptomatic ischemic stroke by Day 28 and unrecognized brain infarction at Day 28. Sample size calculations were performed for detecting a dose-response effect with the MCP-MOD methodology using simulations with the DoseFinding package in R⁴. Simulations of 1000 clinical trials were performed, assuming a true incidence for placebo of 14%, a maximum relative risk reduction of 30% for BMS-986141 8 mg relative to placebo, and relative reductions of 75% and 90% of the maximum for the 0.8 and 4.8 mg doses, respectively. Candidate models included an Emax model and a logistic model.

Initially, randomization will be limited to the two lower doses of BMS-986141 (0.8 mg or 4.8 mg) or placebo in a 1:1:1 ratio until after the DMC review of safety and laboratory data from the Day 28 study visit for at least 10% of planned total subjects (approximately 132 subjects). If the DMC recommends proceeding to inclusion of the highest dose (8 mg), subsequent randomization will be in a 1:1:1:1 ratio. Based on the staggered randomization as shown in in the table below and the assumptions above, the study will have at least 80% power to demonstrate a dose-response relationship, using a 1-sided type I error rate of 15%. A total sample size of 1312 randomized subjects accounts for about 5% of subjects without post-randomization data.

Table 5-1: Randomization Targets

	Placebo	0.8 mg	4.8 mg	8 mg
Prior to interim safety review by the DMC: 132 subjects (1:1:1 randomization ratio)	44	44	44	0
Additional subjects randomized while interim safety reports are being generated and reviewed by the DMC (not included in the DMC safety interim analysis): 100	34	33	33	0

Table 5-1: Randomization Targets

	Placebo	0.8 mg	4.8 mg	8 mg
subjects (1:1:1 randomization ratio)				
After interim safety review by DMC: 1081 subjects	270	270	270	270
Total: 1312 subjects	348	347	347	270

Note: Numbers shown for each treatment group are estimates based on randomization ratio. Actual numbers could be slightly different based on randomization block size and rate of enrollment.

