7.1.2 General Methods for Efficacy Analyses

Generalized Multiple Comparison Modelling (gMCP-Mod)

To demonstrate the dose-response relationship between BMS-986141 treatment (including placebo) and the primary endpoint, the primary analysis will be based on a generalized Multiple Comparisons and Modeling (gMCP-Mod) analysis⁵⁶. This analysis tests for a dose-response relationship, allowing for uncertainty in the dose-response relationship through inclusion of contrasts from multiple pre-specified candidate models to assess dose-response. If a dose-response relationship exists, then fitted estimates for the incidence of the primary endpoint will be calculated in each of the treatment groups using the selected dose-response models.

The gMCP-Mod procedure extends the MCP-Mod methodology to non-continuous endpoints. This is accomplished by decoupling the dose-response model from the expected response through the use of an ANOVA style parameterization of the dose-response parameter. For the binary endpoint used in this study, a logistic regression of the event proportion at each dose level will be used, following adjustment for study time period (1A, 2A, 2B) via the inclusion of an additive covariate. After this first step, the mean parameter estimates from the logistic model and the corresponding covariance matrix, both of which are on the logit scale, will then be used during the rest of the gMCP-Mod procedure. Point estimates from the selected models will be displayed on the proportion scale in all statistical outputs.

Candidate Models and Multiple Testing Procedure

There are two candidate models that will be considered for the primary analysis. These are an Emax model and a logistic model, where dose-response will be tested using dose levels of 0 (placebo), 1, 2, and 2.3 (corresponding to 0.8 mg, 4.8 mg, and 8 mg)⁷.

The MCP-Mod procedure requires certain parameter estimates be pre-specified for the candidate models based on available information in order to derive optimum contrast coefficients for testing the null hypothesis: that a dose-response does not exist in any of the candidate models. It

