7.3.2 Demographic and Baseline Characteristics

The following baseline characteristics will be summarized by treatment group for all randomized subjects, overall, as well as by study time period (1A, 2A, 2B), and for study part 2. All baseline presentations will identify subjects with missing measurements.

- Age (descriptive statistics)
- Age category I, in years (< 65, ≥ 65)
- Age category II, in years (< 65, ≥ 65- < 75, ≥ 75)
- Gender (male, female)
- Race (White, Black or African American, Asian, American Indian or Alaska Native, Native Hawaiian or Other pacific islander, Other)
- Ethnicity (Hispanic/Latino, Non Hispanic/Latino) for US subjects
- Geographical Region (North America, Europe, Asia / Pacific)
- Height, Weight, and BMI
- Acute Ischemic Stroke at Entry (Yes/No)
- National Institutes of Health Stroke Score (NIHSS) at Baseline
- High-risk Transient Ischemic Attack at Entry (Yes/No)
- Lacunar Infarct
- Diabetes mellitus (Yes/No)
- Cigarette use (Yes/No)
- Hypercholesterolemia (Yes/No)
- Hypertension (Yes/No)
- BMI Category (<18, 18-25, 25-30, 30-35, >35)

- Vital signs
- Time since onset of symptoms detected to randomization

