7.5.1.2 Subgroup Analyses

All analyses described in this section will be performed on the ITT Population. Table 7.5.1.2-1 below shows the subgroups of interest for analyses of efficacy data. If the value of the grouping variable cannot be determined for a subject, the subject will be excluded from the corresponding subgroup analysis.

Table 7.5.1.2-1: Subgroups of Interest for Efficacy Assessments

Grouping Variable	Subgroups
Event at entry	Acute ischemic stroke Transient ischemic attack
Time since onset of symptoms detected to randomization	< 24 hours 24 - 48 hours
Lacunar infarct at entry	Yes No
Oxfordshire Community Stroke Project (OCSP) Subtype (only for stroke) at entry	Total Anterior Circulation Stroke (TAC) Lacunar Stroke (LAC) Partial Anterior Circulation Stroke (PAC) Posterior Circulation Stroke (POC)
ABCD2 ^a Score (only for TIA) at entry	4-5 (moderate)

Table 7.5.1.2-1: Subgroups of Interest for Efficacy Assessments

Grouping Variable	Subgroups
	6-7 (high)
Age	< 65 years old ≥ 65 to < 75 years old ≥ 75 years old
Gender	Male Female
Race	White Black or African American Asian Other
Geographic Region	North America Europe Asia / Pacific

^a age, blood pressure, clinical features, duration, diabetes

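### The primary logistic step adjusts for study period only; adding index-event type and time from onset would be a cheap but minor improvement, worth about 0 to 2 points of power

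*SAP*

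**What the plan says.** SAP 7.1.2 estimates the dose logits by logistic regression, "following adjustment for study time period (1A, 2A, 2B) via the inclusion of an additive covariate". Those logits and their covariance matrix then feed the contrast tests. Protocol 8.4.2.1 and the synopsis likewise name one categorical change-point variable as the covariate.

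Three baseline factors are known by the time of randomization:
- **Index event.** The inclusion criteria (Protocol 3.3.1) classify it as stroke or TIA.
- **Lacunar status.** Strokes are subtyped at screening (Protocol 5.8.3), and the IVRS enforces a lacunar cap (Protocol 3.1).
- **Time from onset.** The 48-hour entry window requires it.

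The SAP uses them descriptively. Section 7.3.2 tabulates index event, lacunar infarct and "Time since onset of symptoms detected to randomization". Section 7.5.1.2 makes all three subgroup factors: "Table 7.5.1.2-1 below shows the subgroups of interest for analyses of efficacy data". The sensitivity analyses in SAP 7.5.1.1 include no covariate-adjusted version. Protocol 4.4 and SAP 2.2 state allocation ratios but no stratification factor.

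On power, SAP 5 says "the study will have at least 80% power to demonstrate a dose-response relationship", "using a 1-sided type I error rate of 15" per cent.

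**The concern.** In a binary-outcome model, a pre-specified adjustment for prognostic baseline factors usually gives a somewhat more powerful test and removes the effect of chance imbalance on the dose logits. The design does not otherwise secure balance on these factors, since no strata are stated. The protocol itself suggests that one of them matters: Protocol 3.1 prefers early randomization because recurrence risk is then highest.

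Power has no reserve. The first test already uses a one-sided 15% level, and SAP 7.5.2 requires significance at one-sided 0.025 before MACE is tested. Even a small gain that needs no extra subjects is therefore worth considering.

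**Working it through.** **Inputs from the documents.** SAP 5: "assuming a true incidence for placebo of 14%, a maximum relative risk reduction of 30% for BMS-986141 8 mg relative to placebo". The same section sets the effects at 0.8 mg and 4.8 mg to 75% and 90% of that maximum. Protocol synopsis: "with a total of 1240 evaluable subjects". SAP Table 5-1: arm targets 348/347/347/270. SAP 7.1.2: dose scores 0, 1, 2, 2.3; Emax with half-effect dose 1 and Hill 1; logistic with half-effect dose 1 and steepness 0.1.

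**Step 1: planned rates.** Placebo 14%; 0.8 mg 14 × (1 − 0.30 × 0.75) = 10.85%; 4.8 mg 14 × (1 − 0.30 × 0.90) = 10.22%; 8 mg 14 × 0.70 = 9.8%. Scaling the targets to 1240 gives arms of 328.9, 328.0, 328.0 and 255.2. Expected events are 46.0 + 35.6 + 33.5 + 25.0 = about 140.

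**Step 2: reproduce the plan's power.** Each arm's weight on the logit scale is n·p·(1 − p): 39.6, 31.7, 30.1, 22.6. The logits are −1.815, −2.106, −2.173, −2.220. The Emax shape d/(1 + d) is 0, 0.5, 0.667, 0.697, with weighted mean 0.417. The mean of the Emax contrast statistic, with sign reversed so that benefit is positive, is

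Σ w(m − m̄)(−logit) / √Σ w(m − m̄)² = 6.02 / 3.28 = 1.84.

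For the logistic shape it is 1.76. The two statistics correlate at 0.97, so the multiplicity-adjusted critical value is 1.128. The chance that at least one exceeds it is 78.1%, or 77.8% with the period covariate. Simulation of the same logit-scale test gives 76.1%. Other variants:
- Proportion scale: 77.8% at 1240, 80.1% at 1312.
- Without multiplicity adjustment at 1240: 77.9% (logit), 80.8% (proportion), 79.9% (pooled variance).

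The stated 80% is thus approximately reproduced, but the SAP's own test does not exceed it. At one-sided 0.025 (critical value 2.047), power is 43% to 44%.

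**Step 3: add the baseline factors.** Assumptions: 70% stroke, 20% lacunar, 50% in each onset half; the same strength of odds ratio for each factor; marginal arm rates held at the planned values. Both models include period and are fitted to the same simulated trials (8,000 per row, 4,000 in the first). The Monte Carlo standard error of a single figure at 8,000 trials is about 0.5 point.

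| Odds ratio per factor | c-statistic | Power at 0.15: period only → with factors | Gain | Power at 0.025 |
|---|---|---|---|---|
| 1 | none | 76.4% → 76.3% | −0.1 | 42.8% → 42.9% |
| 1.5 | 0.58 | 76.0% → 76.3% | +0.3 | 41.4% → 42.0% |
| 2 | 0.63 | 75.8% → 76.1% | +0.3 | 41.9% → 42.9% |
| 3 | 0.70 | 75.2% → 76.9% | +1.7 | 41.5% → 43.7% |

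A separate paired simulation (4,000 trials per setting) gave +0.2, +0.7 and +1.2 points at odds ratios 1.5, 2 and 3, and −0.4 with no prognostic value. These runs drew lacunar status independently of index event, so they approximate the nested coding proposed below.

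**Step 4: put the gain in subjects.** Going from 1240 to 1312 subjects raises analytic power from 78.1% to 79.6%, which is 1.5/72 = 0.021 point per subject. A gain of 0.3 point is then worth about 0.3/0.021 = 14 subjects, and 1.7 points about 81.

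**Step 5: chance imbalance.** With 70% strokes, the placebo-to-8 mg difference in stroke share has standard deviation √[0.21 × (1/329 + 1/255)] = 3.8 points. One such deviation moves the crude log-odds difference by roughly 0.038 × ln 2 = 0.026 at odds ratio 2, or 0.038 × ln 3 = 0.042 at odds ratio 3. The planned difference is −2.220 + 1.815 = −0.405, so the shift is about 6% to 10% of it.

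**The case against.** The strongest reply is that the benefit is negligible and rests on assumptions. The documents give no prognostic strength, the gain at modest odds ratios is below the Monte Carlo error of a single power figure, and period is the covariate the design needs, because 8 mg is randomized only in Phase B. This largely stands. It limits the point to an optional improvement.

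Two practical objections also stand. Lacunar status comes from a subtyping done for strokes only (Protocol Table 5.1-1), so separate event and lacunar terms with no coding or missing-value rule could drop TIA subjects from the ITT model. And the change reaches beyond the SAP, because the protocol specifies a single covariate.

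The objection that adjusted logits become conditional is weaker. The period covariate already makes them conditional, and SAP 7.1.2 and 7.5.1 promise results on the proportion scale without saying how period is averaged. A standardisation rule is needed anyway.

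A reader might infer three stronger things that the documents do not support:
- **That adjustment would recover the stated 80%.** A much larger gain would need a c-statistic near 0.76. Under the assumed prevalences, that takes odds ratios of about 4 to 5 for all three factors.
- **That the lacunar cap shows the sponsor expects a different prognosis.** Protocol 3.1 gives only population mix as its reason.
- **That type I error is wholly unaffected.** Control is asymptotic and depends on pre-specification.

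**Conclusion.** The omission is real and its consequence is small. Pre-specified adjustment for index-event type and time from onset should add about 0 to 2 points of power at one-sided 0.15 and about 0.6 to 2.2 points at one-sided 0.025. This assumes odds ratios of 1.5 to 3 per factor and the prevalences in Step 3, none of which the documents supply. If the factors carry no prognostic information, the loss is at most about 0.4 point. It also removes a modest source of chance imbalance.

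In no simulated setting does it bring the SAP's test to 80%. The shortfall in power is a separate matter that this change does not settle. The period-only model is valid, so this is a minor improvement and not a correction of an error.

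**What to change.** Before unblinding, state in SAP 7.1.2 that the logistic step includes:
- study period, as now;
- index-event type as one three-level factor: TIA, lacunar stroke, non-lacunar stroke, using the classification recorded at screening;
- time from onset to randomization, under 24 hours or 24 to 48 hours, as in the subgroup table.

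Add a missing-category rule so that no ITT subject is lost to a missing covariate. The subgroup rule in SAP 7.5.1.2, which excludes undetermined values, should not carry over to the primary model. Use the adjusted dose logits and their covariance in gMCP-Mod, and display incidences standardised over the observed covariate distribution, including period. If the sponsor prefers to leave the primary model alone, add the adjusted model as a sensitivity analysis in SAP 7.5.1.1.

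**Cost.** Text in the SAP, alignment of the covariate statement in Protocol 8.4.2.1 and the synopsis, and a note in the study report, as SAP 7.2.2 requires for changes to planned analyses. No new data or subjects are needed. SAP 2.2 shows that enrolment was still under way when the SAP was written, so pre-specification was feasible. The model has nine parameters (four dose, two period, two index event, one onset) before any missing category, or about 140/9 = 15 to 16 expected events each.

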7.2 Study Conduct

7.2.1 Accrual

The accrual pattern will be summarized per country, investigational site, and per month for all randomized subjects. Enrollment date, randomization date, first dosing date, country, investigational site will be presented in a by subject listing of accrual.

7.2.2 Relevant Protocol Deviations

Relevant deviations from the study protocol will be documented and accounted for in presenting the data summaries, listings and descriptive statistical analyses. Any changes from planned protocol-specified analyses will be defined in the SAP and reported in the CSR. The relevant protocol deviations are described in the table below.

Table 7.2.2-1: List of Relevant Protocol Deviations

Number	RPD Criteria
1	Subject randomized but not dosed
2	Error in treatment assignment (resulting in a subject receiving a treatment other than that assigned by the IVRS) during the first 28-day interval
3	Poor treatment compliance for either BMS-986141 or ASA (compliance less than 80% or more than 120%) during first 28-day interval
4	Randomized subjects with history of atrial fibrillation (AF) other than transient AF related to cardiac surgery at enrollment (per Exclusion Criteria 1a from the protocol)
5	Randomized subjects with unrecognized or misdiagnosed intracranial hemorrhage (ICH) as determined by the central reader based on the baseline study specific MRI (presence of type 1 or 2 parenchymal hematoma)
6	Randomized subjects who took no dose of ASA or dose of ASA not within limits designated by the protocol for ≥ 5 consecutive days in the first 28 days of the treatment period
7	Randomized subjects who took oral anticoagulants or prohibited antiplatelet therapy, other than study medication, for > 2 consecutive days during the first 28days of the treatment period
8	Randomized subjects that were treated with a strong CYP3A4 inhibitor for > 5 days during the first 28 days of the treatment period ^a

a: CYP3A4 inhibitors will be defined in a separate file maintained by the study team and will be classified as weak, moderate, or strong.

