3.4 Concomitant Treatments

3.4.1 Prohibited and/or Restricted Treatments

Any investigational drug or placebo exposure during and 60 days post study drug administration is prohibited.

Use of the following treatments is prohibited during the treatment period:

- Anticoagulants including warfarin or other vitamin K antagonists, oral thrombin and factor Xa inhibitors, bivalirudin, hirudin, argatroban, unfractionated and LMWH, with the exception of heparin or LMWH used to maintain patency of indwelling catheters or for prophylaxis of VTE
- Antiplatelet therapy other than study medication or ASA at a dose from 75 to 162 mg/day including ASA at a dose < 75 mg/day or > 162 mg/day, GPIIb/IIIa inhibitors, clopidogrel, ticlopidine, prasugrel, dipyridamole, ozagrel, cilostazol, and ticagrelor
- Requirement for treatment with concomitant oral or intravenous therapy with strong CYP3A inhibitors or CYP3A4 inducers
- Ongoing treatment with non-steroidal anti-inflammatory drugs (NSAIDs); COX-2 inhibitors are allowed

For WOCBP the use of hormonal contraceptives should not be the primary method of contraception; women may continue on these medications but must commit to using another method of highly effective birth control while on study. See [Section 3.3.1](#).

The following medical procedures are prohibited while the subject is receiving study medication: carotid revascularization such as endarterectomies and stenting.

If treatment with the therapies noted above, except for strong CYP3A4 inhibitors or strong CYP3A4 inducers, becomes necessary, the study medication should be stopped temporarily up to a maximum of 14 days while subjects are treated with the prohibited medications. Study medication should be restarted upon completion of treatment with the prohibited therapy. Subjects who will require treatment with strong CYP3A4 inhibitors or strong CYP3A4 inducers must be discontinued from study treatment. It is recommended the strong CYP3A4 inhibitor or inducer is not started until at least 24 hours after the last dose of study medication. For guidance related to dosing of study medication, please refer to [Section 4.5](#).

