5.4.1 Symptomatic Stroke

All cases of suspected recurrent stroke will be adjudicated by a blinded Clinical Events Adjudication Committee (CEC). Further information regarding the CEC and its processes are detailed in the CEC Charter.

Diagnosis of stroke will require the abrupt onset of focal neurological symptoms lasting at least 24 hours or identification of an acute, new infarct by CT or MRI in subjects with symptoms lasting less than 24 hours. Evaluation and treatment of strokes will be according to the local standard of care. It is strongly recommended (but not required) that an imaging procedure such as a CT scan or MRI be performed to evaluate events of suspected stroke or TIA. Adjudicated strokes will be categorized by the CEC as definite ischemic, definite hemorrhagic, hemorrhagic transformation or type uncertain. Additional classification of stroke subtypes will be specified in the CEC charter.

Evaluation of suspected TIA events should be performed according to the local standard of care. If a TIA is considered to be a suspected stroke event by the investigator, the procedure for reporting a suspected stroke event should be followed and the event will be adjudicated.

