8.4.2 Efficacy Analyses

8.4.2.1 Primary Efficacy Endpoint Analysis

To demonstrate the dose-response relationship between BMS-986141 treatment (including placebo) and primary endpoint, the primary analysis will be based on a Multiple Comparisons and Modeling (MCP-Mod) analysis.^{15,16} This analysis tests for a dose-response relationship, allowing for uncertainty in the dose-response relationship through inclusion of contrasts from two pre-specified candidate models to assess dose-response. If a dose-response relationship exists, then fitted estimates for the incidence of the primary endpoint will be calculated in each of the treatment groups using the selected dose-response model, or using a weighted model-averaging method if significance is detected using both models. Candidate models will include an Emax model and a logistic model, where dose-response will be tested using dose levels of 0 (placebo), 1, 2, and 2.3 (corresponding to 0.8 mg, 4.8 mg, and 8 mg)¹⁷. The parameters used to determine the contrast for testing will include assumed placebo event rate 14% and maximum risk reduction of 4.2%. For the Emax model, the parameters used will be 1.0 for the dose corresponding to half of the maximum effect and 1.0 for a “Hill” parameter that determines the steepness of the model at the dose of half effect. For the logistic model, the initial parameters used will be 1.0 for the dose corresponding to half effect and 0.1 for the parameter that determines the steepness of the curve.

The incidence of the composite of adjudicated symptomatic recurrent ischemic stroke by Day 28 and unrecognized brain infarction at Day 28 will also be summarized by treatment. Point

estimates and 95% CIs for event rates will be presented by treatment, together with point estimates and 95% CIs for the relative risk reduction between each BMS-986141 arm and placebo.

A single categorical variable based on study change points (length of treatment [28 or 90 days] and randomization phase [randomized prior to or after DMC safety interim analysis decision]) will be included as a covariate.

A sensitivity analysis will include subjects who are randomized, treated, and with an evaluable MRI at Day 28, or an adjudicated symptomatic recurrent stroke by Day 28.

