6.3 Populations for Analyses

The analyses will use several populations as defined below.

- 1) All Enrolled Subjects: Includes all subjects who signed informed consent.
- 2) All Randomized Subjects / Intent to Treat (ITT) Population: Includes all subjects who were randomized to a treatment, regardless of whether they received study drug or not. This population will be analyzed according to the treatment assigned at randomization.
- 3) All Evaluable Subjects: Includes All Randomized Subjects as above, excluding those subjects' visits where relevant protocol deviations occurred, as defined in [Section 7.2.2](#).
- 4) All Treated Subjects: Includes all subjects who received at least one dose of study medication. This will be the primary population used in safety analyses and will be analyzed according to the treatment assigned at randomization, except in the following cases:
 - If a subject received the same incorrect treatment throughout the study (until either Day 28 or Day 90, or until discontinuation of the study drug), then the subject will be analyzed based on the treatment received.

- If a subject received study drug from more than one treatment group, and none of the administrations were consistent with the assigned randomized treatment group, then the subject will be analyzed based on the first treatment received.
- 5) Pharmacodynamics (PD) Population: A subset of the ITT Population that includes subjects with at least one pharmacodynamic endpoint assessed following the first dose of BMS-986141.
 - 6) Pharmacokinetic (PK) Population: Includes all subjects treated with BMS-986141 who also have at least one post-dose PK sample. The Evaluable PK Population is further defined as a subset of the PK Population including subjects who have adequate PK profiles on Day 1.

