7.5.1.1 Sensitivity Analyses

To assess the robustness of the primary efficacy analysis, additional sensitivity analyses will be carried out using the following approaches:

- Following the same procedure as the primary analysis, considering the All Evaluable Subjects population in place of the All Randomized Subjects population.
- A worst-case analysis that will repeat the primary analysis on the ITT population where any missing information that is consequential to the evaluation of the primary endpoint will be considered as an event.

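### SAP deviation items 6 and 7 do not require the deviation to precede the primary event, so treatment given because of a stroke can decide who is in the Evaluable sensitivity analysis

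*SAP*

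**What the plan says.** SAP 7.2.2, Table 7.2.2-1, lists the relevant protocol deviations. Item 7 covers a randomized subject if they "took oral anticoagulants or prohibited antiplatelet therapy, other than study medication, for > 2 consecutive days during the first 28days of the treatment period". Item 6 covers those who "took no dose of ASA or dose of ASA not within limits designated by the protocol for ≥ 5 consecutive days" in the same 28 days. Both have a minimum run and a window. Neither refers to the date of the primary event.

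SAP 6.3 builds the Evaluable population from all randomized subjects, "excluding those subjects' visits where relevant protocol deviations occurred". SAP 7.5.1.1 uses it for the first of two sensitivity analyses, which repeats the primary analysis "considering the All Evaluable Subjects population in place of the All Randomized Subjects population".

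The protocol makes such treatment after a stroke foreseeable. Section 5.4.1: "Evaluation and treatment of strokes will be according to the local standard of care". Section 3.4.1 provides that if most of the prohibited therapies become necessary, "the study medication should be stopped temporarily up to a maximum of 14 days while subjects are treated with the prohibited medications", with study drug restarted afterwards.

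The protocol's own sensitivity analysis (8.4.2.1) takes randomized and treated subjects "with an evaluable MRI at Day 28, or an adjudicated symptomatic recurrent stroke by Day 28". SAP 7.5.1.1 does not list it.

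**The concern.** A deviation rule for a supportive analysis should pick out departures that could distort the treatment comparison. It should not pick out consequences of the endpoint. Take a subject with an adjudicated ischemic stroke on Day 6 who is moved from ASA to another antiplatelet agent. Three days on the new agent meets item 7, and five days without ASA meets item 6. Both arise because the endpoint occurred. A comparable subject without a stroke has no such reason to be switched.

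At stake is the usefulness of one robustness check. If membership of the Evaluable set depends on the outcome, a gap between this analysis and the ITT result may reflect the selection rule rather than protocol adherence. Symptomatic strokes are the events exposed to this. Silent infarcts are read centrally and those readings are not returned to sites (Protocol 5.3.1).

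**Working it through.** **1. The plan's own figures.** Placebo 14% and a 30% reduction at 8 mg give 0.14 × 0.70 = 9.8%, a 4.2-point difference, matching SAP 7.1.2. The reductions at 0.8 and 4.8 mg are 75% and 90% of that, giving 10.85% and 10.22%. With allocation 348/347/347/270 scaled to 1240 evaluable subjects, 140.2 primary events are expected. An analytic power calculation for the two-contrast test at one-sided 0.15 gives 78.1% at 1240 and 79.6% at 1312, against the stated minimum of 80%. Other variance choices and a simulation at 1240 give 75.2% to 78.1%. The point does not rest on this small gap.

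**2. Which strokes can trigger the items.** Item 7 needs at least 3 consecutive days inside 28, so therapy must start by Day 26 (28 − 3 + 1). Item 6 needs 5, so the gap must start by Day 24 (28 − 5 + 1). Item 3 (compliance below 80%) can follow too: 6 missed days give 22/28 = 78.6%, if interrupted days count in the SAP 7.4.2 calculation. Permanent stopping does not count there, because the 28-day compliance window ends at the last dose.

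**3. What removing visits does to one composite per subject.** The SAP does not say. There are two readings.

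- *Reading A, endpoint removed.* Let ps be the symptomatic rate, pm the MRI-only rate and f the share of strokes triggering an item. Other deviations are ignored. Evaluable rate = [ps(1 − f) + pm] / (1 − ps·f).
- *Reading B, only the Day 28 MRI visit removed.* SAP 4.1 then applies. A stroke still makes the composite an event; with no stroke, the composite is missing. If a share d of stroke-free subjects deviate, regardless of MRI result, the rate becomes [ps + pm(1 − d)] / [1 − d(1 − ps)]. This exceeds ps + pm by d·ps(1 − ps − pm) / [1 − d(1 − ps)]. With ps = 0.04 and pm = 0.10 the excess is 0.0344d / (1 − 0.96d): upward, where Reading A goes downward.

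**4. Numbers for Reading A.** The documents give neither the component split nor f. Assumed: placebo ps = 4% (range 3-6%) and pm = 10%, with f from 30% to 80%.

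- Placebo events in 348 randomized: 348 × 0.14 = 48.7.
- Lost: 348 × 0.04 × 0.3 = 4.2 to 348 × 0.04 × 0.8 = 11.1. Over the wider range: 348 × 0.03 × 0.3 = 3.1 to 348 × 0.06 × 0.8 = 16.7.
- Placebo rate: 0.128/0.988 = 13.0% to 0.108/0.968 = 11.2%.

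Relative risk reduction (RRR) at 8 mg, true value 30% in each row:

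| Active ps + pm | f = 30% | f = 80% |
|---|---|---|
| Equal effect: 2.8% + 7.0% | 1 − 0.0904/0.1296 = 30.3% | 1 − 0.0773/0.1116 = 30.7% |
| Mainly symptomatic: 1.0% + 8.8% | 1 − 0.0953/0.1296 = 26% | 1 − 0.0907/0.1116 = 19% |
| MRI-only: 4.0% + 5.8% | 1 − 0.086/0.128 = 33% | 1 − 0.066/0.108 = 39% |

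**5. Wider assumptions.** Suppose symptomatic strokes are 20-50% of events, 25-100% of them are removed, and the shares are equal across arms. Then 7 to 70 of the 140.2 events go. The odds ratio is unchanged, the RRR is 30.2-31.6%, and power for this sensitivity analysis falls from 78.1% to between 76.9% and 61.3%.

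**The case against.** The strongest reply starts from SAP 6.3, which removes visits, not subjects. The stroke component is a committee-adjudicated event, not a visit result, and SAP 4.1 lets it stand when the MRI component is unavailable. A reader might infer that stroke subjects are certain to be dropped; the text does not establish that. What stands is that Reading B loses no strokes. It still does not make the rule neutral, because deviators then stay or become missing according to whether they had a stroke. Visit wording also does not fit subject-level items such as 1, 4 and 5.

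A reader might also infer that items 6 and 7 have no time limit. They do: a 28-day window and a minimum run. What is missing is a condition relative to the event. The term treatment period is itself unclear. SAP 6.1 gives 28 days for Part 1, while SAP 7.4.4 ends on-treatment medication at the last dose. On the narrower sense, therapy begun after permanent discontinuation escapes. Where study drug is interrupted and restarted under Protocol 3.4.1, the therapy counts on either sense.

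Third, a reader might conclude that the robustness assessment as a whole is lost. It is not. The primary analysis is ITT (SAP 7.5), the worst-case analysis keeps every observed event, and SAP 7.5.3 analyses each component separately. No alpha rests on the Evaluable set.

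Fourth, the unequal-effect rows are illustrations. One needs a 75% reduction in symptomatic stroke with 12% on MRI-only lesions; the other needs 0% and 42%. The documents state no component-specific effect, and with equal effects the RRR hardly moves.

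Finally, because SAP 4.1 sets a subject with no MRI and no stroke to missing, the SAP's primary analysis set is already close to the protocol's sensitivity set, which mainly adds the condition of having been treated. So the omission costs little in substance. It remains an undeclared difference, although SAP 7.2.2 says that changes from protocol-specified analyses will be defined in the SAP.

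**Conclusion.** The point holds as a defect in one sensitivity analysis that should be corrected. Items 6 and 7 can be met by treatment given because of the primary event, and the SAP does not define how a deviation acts on the composite. On both plausible readings, membership of the analysis set depends on the outcome, with the placebo rate moving down on one and up on the other.

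On the endpoint-removed reading, about 4-11 of about 49 placebo events are lost (3-17 over the wider range). This rests on an assumed component split and an assumed share of strokes triggering an item. The RRR is almost unchanged if effects are equal on both components and can be biased either way if they differ. The ITT primary, worst-case and component analyses are untouched. Item 8 (strong CYP3A4 inhibitors) is not part of the point, since the documents do not link it to stroke treatment.

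**What to change.** Before unblinding:

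1. In SAP Table 7.2.2-1, count items 6 and 7 only when the deviation starts before the first adjudicated primary-endpoint stroke, or before the Day 28 MRI if there is none. Apply the same limit to item 3 only where non-compliance results from an interruption after a stroke.
2. In SAP 6.3, state that a relevant deviation excludes the subject's composite endpoint as a whole, and that a subject with an adjudicated ischemic stroke by Day 28 is not excluded for treatment given afterwards.
3. In SAP 7.5.1.1, restore the sensitivity analysis of Protocol 8.4.2.1 or declare and justify the change. Amend SAP 7.5, which puts all efficacy analyses on ITT, to allow for the Evaluable analysis.

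The cost is SAP wording and some extra date programming, mostly for item 3, where compliance must be recalculated up to the stroke date. Event, dosing and concomitant-medication records are already collected, and no clinical rule changes. A stroke subject will still have had less time in which to deviate beforehand, so the analysis remains supportive only.
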